	Level 3 (cluster)	0.01 to 0.15	0.27
Alpha		0.05	0.05
Power		0.80	0.80
One-sided or two-sided?		Two	Two
Average cluster size		2 CYP per family	1.4 CYP per family
Number of clusters	Intervention	175	125
	Control	175	125
	Total	350	250
Number of participants (CYP)	Intervention	350	175
	Control	350	175
	Total	700	350

The power analyses published in the protocol included key parameters for which no empirical estimates could be obtained. Specifically, these were covariate explanatory power (from the baseline mothers SDQ measure) at CYP and family levels and the family level ICC for the mothers SDQ measure at outcome. The protocol used relatively wide ranges of values for CYP and family level explanatory power (between 0.25 and 0.49) and ICC (0.01 to 0.15).

As specified in the protocol, analyses of data from the internal pilot provides empirical point estimates for these parameters for use in the updated power analyses presented here. At the time of writing (August 2024), a total of 43 families (21 allocated to MBT and 22 to TAU) with 61 CYP (30 MBT, 31 TAU) had complete baseline/T1 and outcome (T2, post intervention) mothers SDQ. Analyses of these 61 CYP in 43 families has been used to provide empirical estimates for ICC and explanatory power at the family and CYP levels.

The power analyses were undertaken using equation 1.0 below and checked using the PowerUp! software (Dong & Maynard, 2013, sheet CRA2_2r).

$$[1.0] \quad MDES_{2LCRT} \sim M_{J-m-2} \sqrt{\frac{1}{P(1-P)}} \sqrt{\frac{ICC(1-R_{Fam}^2)}{J} + \frac{(1-ICC)(1-R_{CYP}^2)}{nJ}}$$

For a 2-level CRT design, the MDES is influenced by (estimates updated from analyses of pilot data):

- n=number of CYP per family = **1.4** (updated from 2.0 in protocol).
- J = number of families (**90** at pilot, allowed to vary up to **400** see below).
- P = proportion of families allocated to intervention group (= **0.50**).
- m= number of (level 2) covariates used (which will include: group membership, family-level pre-test, 4 (dummy) variables used for minimisation ~ **6** variables).
- M_{J-m-2} is the group effect multiplier value of the t-distribution for a 2-tailed test with alpha=0.05 & beta=0.80.
- ICC is the family level ICC = **0.27** (updated from 0.01 to 0.15 in protocol). This is the proportion of variance of the outcome at level 2 (between-family variance).

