The updated power analyses presented here illustrate that, even with fewer CYP per family than initially estimated, a smaller sample of families is likely to be sufficient sensitivity to detect an MDES of 0.20 sds or higher than was estimated at protocol. With 250 families (and 350 CYP), the MDES estimate is 0.17 sds. With an attrition rate of 10%, assuming attrition was random, the indicative MDES estimate is 0.18 sds. With an attrition rate of 20%, assuming attrition was random, the indicative MDES estimate is 0.19 sds.

Therefore, following the updated power analysis, the recommended sample size for the evaluation of the Tavistock MBT-PP programme is reduced from 350 families (700 CYP) to be 250 families (350 CYP).

Analysis

Research questions were operationalised as follows:

RQ1 Does MBT-PP (compared to TAU) delivered to parents experiencing IPC lead to lower externalising and internalising behaviours in children aged 8-14 (as measured by the SDQ total 'difficulties' scale)?

This splits into two separate RQs (SDQ total difficulties for mothers and for fathers).

RQ1a Does MBT-PP (compared to TAU) delivered to parents experiencing IPC lead to lower externalising and internalising behaviours in children aged 8-14 as measured by the mother's SDQ total 'difficulties' scale? – PRIMARY OUTCOME RQ1

RQ1b Does MBT-PP (compared to TAU) delivered to parents experiencing IPC lead to lower externalising and internalising behaviours in children aged 8-14 as measured by the father's SDQ total 'difficulties' scale? – SECONDARY OUTCOME RQ1

RQs 2-8 inclusive also all examine secondary outcomes, and, apart from those where the outcome variable comes from CYP rather than parents (RQ2 regarding child wellbeing and RQ4 regarding child perception of IPC), they split into a) maternal report and b) paternal report, as per RQ1.

RQ2 Does MBT-PP (compared to TAU) delivered to parents experiencing IPC lead to higher wellbeing in children aged 8-14 (as measured by the Stirling Children's Well-being Scale)?

RQ3 Does MBT-PP (compared to TAU) delivered to parents experiencing IPC lead to lower IPC reported by parents (as measured by the O-Leary-Porter Scale)?

RQ3a Does MBT-PP (compared to TAU) delivered to parents experiencing IPC lead to lower IPC reported by mothers (as measured by the O-Leary-Porter Scale)?

RQ3b Does MBT-PP (compared to TAU) delivered to parents experiencing IPC lead to lower IPC reported by fathers (as measured by the O-Leary-Porter Scale)?

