The analysis described in this plan follows YEF analysis guidance¹. An Intention to Treat (ITT) approach will be taken whereby CYP are identified as members of the intervention or control group solely based on their random allocation and regardless of whether their parent(s) participate in the intervention or not. The ITT approach best preserves random allocation. This means that the only difference between the two group (of families/parents) is that one group received the Tavistock MBT-PP programme and the other groups (TAU) did not. All other differences between these groups are (fixed to be) random at baseline and, assuming zero attrition, this assumption is maintained at outcome. It is the ITT analysis of the primary outcome (mothers reported SDQ total difficulties score) that this clustered RCT is statistically powered to detect. Specifically and assuming zero attrition, if a difference between the intervention and control group is observed to be 0.17 sds or higher, this would represent evidence that participation in the Tavistock programme caused this positive (or negative) impact within pre-specified levels of statistical significance ($p < 0.05$, two-tailed) and statistical power (0.80 or higher). As detailed below, following the ITT analysis of the primary outcome, missing data and Compliers Average Causal Effect (CACE) analyses will be undertaken.

An ITT approach will also be used for analyses of secondary outcomes. Follow-on analyses of the primary outcome will estimate the Compliers Average Causal Effect (CACE); the impact of the programme for CYP located in families/parents known to have engaged in the MBT-PP programme as was intended (see below).

All analyses will be undertaken using STATA v18. Specifically, parameter estimates will be obtained using the 'mixed' suite of commands in the STATA software. For primary and secondary outcomes, pre-test covariates will be included at both CYP and cluster (family) levels. These will be centred as recommended by Hedges & Hedberg (2007 & 2013) and Konstantopoulos (2008). Specifically, at the CYP level, scores will be centred around the cluster (family/parent) mean and at the family/parent level the cluster(family) means will be centred around the overall cluster-level grand mean. Other than the constant term, centring

¹ <https://youthendowmentfund.org.uk/resources-for-evaluators/>

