Structural equation modelling (SEM) is the most appropriate technique with which to test these models because unlike path analysis it enables us to estimate measurement error within the model. The SEM analyses will be conducted using the Lavaan package in R. MBT and TAU groups will be included in the analyses together with the initial analysis fitting the same model to both groups with all parameters set to be free and model parameters being generated for each group separately. Fit of all models tested will be appraised using commonly used fit indices. Fit for the whole model and the models for each group will be determined with chi-square, CFI, RMSEA, SRMR, and AIC. Following Hu and Bentler (1999) the following criteria will be used to determine good fit (CFI > .95; RMSEA < .06; and SRMR < .08).

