Before comparing latent parameters across the groups, we will examine measure invariance across the groups. Due to the random allocation of CYPs and parents to the MBT and TAU groups we would not expect differences between the groups in terms of interpretations of the constructs being measured. However, as the groups will have differing experiences during the intervention period, particularly in relation to aspects of mentalising examining measure invariance is advised prior to comparing latent variable means and variances across the two groups. We will undertake this invariance testing by examining configural variance, metric invariance and scalar invariance (see Putnick & Bornstein, 2016). Configural invariance checks that the model structure is equivalent across the groups and is tested by allowing the various parameters in the model to be free across the groups. Metric invariance ensures that, for both groups, each of the observed variables contributes to their relevant latent variables to an equal degree. This is assessed by constraining the various factor loadings to be equivalent across the groups. Scalar invariance tests the degree to which the latent variables are measured on the same scales and that any differences between the group means of the latent variables is captured by the differences of the means (intercepts) of the observed variables. This is assessed by specifying that item intercepts are equivalent across the groups. The test of measure invariance involves comparing the three modes outlined above (the configural, metric & scalar models) and undertaking likelihood ratio tests which compare chi-square statistic for the metric test model with the configural model and then a further test comparing the scalar model with the metric model. If either of these two tests is significant then this suggests potential problems with measure noninvariance. In the case of noninvariance an exploration of the models would be conducted to try to identify possible reasons for noninvariance. In the case of noninvariance we might not be able to then compare the latent

means across the two groups. In such a scenario we would test the models in each group separately and not directly compare any parameters across the two groups.

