If the assumption of measure invariance is upheld, we will look to compare latent means across group with a particular focus on the mentalising latent variables as these are the key targets of the MBT intervention. This would be undertaken by restricting the models to have equal means in the mentalising latent variables and then conducting likelihood ratio tests to compare this constrained model with the model where the means are free to vary. If the likelihood ratio test is not significant then this would suggest that groups do not differ in terms of these latent means. We would also compare the regression coefficients from the mentalising latent variables to the anger expression latent variable in a similar way.

We will first utilise the above method to test a model featuring post-intervention SDQ-TD score (mothers) as the final endogenous variable in the causal chain. We will then test the same models with child well-being score at post-intervention as the final endogenous variable (figures 3 and 4). We will repeat this whole process using fathers' SDQ-TD scores. We will run these SEM models even in the absence of a main effect on each final endogenous variable, because it is possible to detect indirect effects in the absence of a direct effect, and indeed important to do so to provide information as to why the main effect is present or not (O'Rourke & Mackinnon, 2018).

Additionally, if there are sufficient responses from the three month follow-up testing for the primary (child internalising and externalising behaviours) and secondary (child psychological well-being) measures we will re-test the models in Figures 1 & 3 (and if possible Figures 2 & 4) but with replacing the post-intervention measures of these primary and secondary outcome with the three-month follow-up measures of these variables. This potentially enables us to test whether changes to mentalising, anger expression, interparental conflict and parenting style at time 2 predicts child behaviour and well-being at follow-up and thus potentially further supporting any causal relationships established from the post-intervention SEM modelling.

Figure 3. Proposed causal model for SEM analysis with the secondary outcome measure of child psychological well-being.

[figure not shown]
[figure not shown]

Figure 4. Proposed causal model for SEM analysis for separated parents with the secondary outcome measure of child psychological wellbeing, including the parental emotional adaptation measure.

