Compliance will be measured at the family level and is defined as families where at least one parent received 6+ sessions of MBT-PP (i.e., a family where two parents received up to 5 sessions each would not be classed as compliant). Six sessions is selected as the cut off due to previous research finding significant effects when 6 sessions was used as the minimum clinical offer (Hertzmann et al., 2016)

Compliance is assumed to be one-sided. Specifically, whilst it is possible for a family allocated to the MBT group to have not met the pre-specified compliance criteria (i.e., attending 6+ MBT-PP sessions), it is not possible for families allocated to the TAU group to have experienced any of the MBT-PP programme.

Compliance will be operationalised as a family-level binary variable which identifies CYPs in families classed as ‘compliant’ (= 1) and ‘not compliant’ (= 0). This will be used for the Compliers Average Causal Effect (CACE) analysis. An instrumental variable (IV) approach will be used with two-staged least squares to obtain CACE estimates. The first stage models the compliance binary outcome with the treatment indicator (T_j) included as a covariate. The predicted value for the compliance outcome (C'_j) is then entered into a second stage model in place of the treatment indicator (T_j) as described in equations 6.1 (step 1) and 6.2 (step 2) below.

$$[6.1] \quad C_j = \beta_0 + \beta_1 T_j + \beta_2 (X_{ij} - \bar{X}_j) + \beta_3 (\bar{X}_j - \bar{X}) + \beta_{4..7} [MIN DUM]_j + \vartheta'_j + \varepsilon'_{ij}$$

$$[6.2] \quad Y_{ij} = \beta_0 + \beta_1 C'_j + \beta_2 (X_{ij} - \bar{X}_j) + \beta_3 (\bar{X}_j - \bar{X}) + \beta_{4..7} [MIN DUM]_j + \vartheta'_j + \varepsilon'_{ij}$$

These two stages are included in the STATA ‘ivregress’ command. Standard errors of estimates will be adjusted for clustering of CYP in families using the ‘vce (cluster robust)’ subcommand.

Intra-cluster correlations (ICCs)

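### The theory-of-change SEM makes no allowance for children nested in families; if child rows carry shared parent scores, its chi-square and likelihood ratio tests reject too often

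*SAP*

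**What the plan says.** All of the SEM text is in the SAP section on testing the theory of change mechanisms.

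- **Software.** "The SEM analyses will be conducted using the Lavaan package in R". No estimator, cluster variable, robust or scaled test, two-level SEM or one-row-per-family rule is given.
- **Invariance.** Metric and scalar invariance are judged by "undertaking likelihood ratio tests which compare chi-square statistic for the metric test model with the configural model", then scalar against metric. A significant result on either test is read as possible noninvariance.
- **Consequence.** The analysts would first explore the reasons. They might then be unable to compare latent means. If so: "In such a scenario we would test the models in each group separately and not directly compare any parameters across the two groups".
- **Arm comparison.** If invariance holds, mentalising means are compared by "conducting likelihood ratio tests to compare this constrained model with the model where the means are free to vary". The mentalising-to-anger coefficients are compared similarly.
- **Repeats.** The process is repeated for child well-being, fathers' SDQ, separated parents and, data permitting, three-month follow-up.

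Elsewhere the SAP does handle clustering. Equations 2.0 to 5.0 carry a family random effect, as does the missingness model. For the CACE, "Standard errors of estimates will be adjusted for clustering of CYP in families". On size: "With 250 families (and 350 CYP), the MDES estimate is 0.17 sds".

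**The concern.** An ordinary chi-square or likelihood ratio test assumes independent rows. Every SEM here ends in a child outcome. The protocol collects the SDQ for each child, and SAP equation 3.0 indexes every secondary outcome, parent scales included, by child within family. An analyst following the SAP would therefore most naturally build a file with one row per child.

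Mentalising, anger, parent-reported conflict and parenting style are parent reports. If each parent has one score on these, a two-child family contributes the same parent twice. The test statistic grows and the reference distribution does not.

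Two results are at stake. The invariance tests would fail too often when invariance is true, which pushes the analysis towards the branch with no comparison between arms. When the comparison does go ahead, the test of mentalising, which the SAP treats as the main target of the therapy, would have an inflated false-positive rate.

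**Working it through.** **Inputs from the SAP (sample size section).** 250 families, 125 per arm; 350 CYP; 1.4 CYP per family; family ICC 0.27; R² 0.75 (child) and 0.61 (family); 6 family-level covariates; equal allocation. The SAP gives no df, alpha or power for the SEM tests.

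**Assumptions.** (a) Rows are children. (b) Each parent-level score is identical for all siblings. (c) Family-size mixes average 1.4; the SAP gives only the mean. (d) Tests are at 5%. (e) The df values are illustrative.

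**1. The SAP's own figure.** Equation 1.0 at J = 250, with a multiplier of about 2.81 on 242 df:

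- between-family term: 0.27 × 0.39 / 250 = 0.000421
- within-family term: 0.73 × 0.25 / 350 = 0.000521
- MDES = 2.81 × 2 × √0.000943 = 0.173

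The SAP states 0.17, so the cluster inputs are read correctly.

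**2. Inflation factor.** With m children per family and identical sibling scores, the likelihood ratio statistic behaves approximately as c times a chi-square, with c = Σm² / Σm.

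- 60% one child, 40% two: c = 2.2 / 1.4 = 1.57. This is the smallest value possible with whole-number family sizes averaging 1.4.
- 70% one, 20% two, 10% three: c = 2.4 / 1.4 = 1.71.

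**3. False-positive rate of a nominal 5% test.** This is P(χ² on df > 95% critical value / c). At 1 df and c = 1.57, the threshold is 3.84 / 1.57 = 2.44 and the rate is 11.8%.

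| df | c = 1.57 | c = 1.71 |
|---|---|---|
| 1 | 11.8% | 13.4% |
| 3 | 17.4% | 20.7% |
| 5 | 21.7% | 26.4% |

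**4. Either invariance test failing falsely, 5 df each, treated as independent.**

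- c = 1.57: 1 − (1 − 0.217)² = 38.7%
- c = 1.71: 1 − (1 − 0.264)² = 45.9% (from unrounded rates)
- nominal: 1 − 0.95² = 9.75%

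**5. Simulation check.** Two-group, one-factor, six-item maximum likelihood model; 125 families per arm (75 with one child, 50 with two); no true arm difference; 1,500 runs.

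| Test | Child rows | One row per family |
|---|---|---|
| Metric (5 df) | 23.7% | 4.9% |
| Scalar (5 df) | 22.5% | 5.3% |
| Either | 41.5% | 10.0% |
| Latent mean (1 df) | 11.9% | 6.1% |

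The child-row results agree with the formula, and one row per family restores the nominal level. Scaled tests with family as cluster were not simulated here.

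**6. Measures that differ between siblings.** With ICC 0.27 the factor for means is 1 + 0.27 × (c − 1) = 1.15 to 1.19. A 5% test becomes about 7% at 1 df and 9-10% at 5 df, a much smaller problem.

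**The case against.** The strongest reply is that this is under-specification rather than a demonstrated wrong test.

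- **Row unit.** The SEM section does not state it, the model figures are not shown, and the baseline-balance section does use family-level aggregates. A reader might infer that the SAP definitely analyses child rows. It does not say so. Child rows remain the natural reading, and if one row per family was meant, that rule is missing too.
- **Shared parent scores.** The documents do not say whether the parent scales are answered once or once per child. Equation 3.0 centres each score on its family mean, which is empty if siblings share a score. So the large figures are conditional on assumption (b).
- **The noninvariance rule.** A reader might infer that a failed test cancels the arm comparison. The text puts exploration first and hedges the outcome. A false failure makes that outcome more likely, not automatic.
- **Larger numbers.** At 15 df each, the chance of at least one false failure would be about 63-73%, but that describes a stand-alone mentalising model for one parent. Expected RMSEA of √(2(c − 1)/350) = 0.057 to 0.064, around the SAP's 0.06 cut-off, holds only for a purely parent-level model. The planned models all contain child outcomes, so neither figure can be claimed for them.
- **Consequences.** The protocol calls the mediation models exploratory. Arm differences on each mentalising subscale are also tested separately, for mothers and fathers, with a family random effect.
- **Remedy.** If the indicators are items, the scales give 18 + 7 + 10 + 8 + 13 + 20 = 76. Loadings, intercepts and residual variances come to about 228 parameters per arm, against 125 families. A family-clustered robust test may then be unstable.

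All of these points stand as limits. None supplies the missing allowance for clustering.

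**Conclusion.** The concern holds in conditional form. The SEM section specifies ordinary chi-square and likelihood ratio tests and is silent on clustering, in a SAP that handles clustering in its impact, missingness and CACE models.

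Under child rows, shared parent scores and family-size mixes averaging 1.4, a 5% test on parent-level variables runs at about 12-13% (1 df), 17-21% (3 df) or 22-26% (5 df). The chance that at least one invariance test fails falsely is about 39-46% at 5 df each, against about 10%. The mentalising comparison probably has more than 1 df, because the SAP refers to several mentalising latent variables. The actual df is unknown. For measures that vary between siblings, the rate is roughly 7-10%.

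The SEM section states no error rate of its own, so the comparison is with a conventional 5%, not with a promise in the plan. The primary SDQ estimate is not touched. The SAP should be changed before the mechanism analysis is run.

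**What to change.** In the SAP section on testing the theory of change mechanisms:

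1. State the row unit of every SEM, and whether each parent scale is answered once per parent or once per child.
2. For invariance, latent-mean and path tests that involve only parent-level variables, use one row per family.
3. For models that include child outcomes, declare family as the lavaan cluster, use the MLR estimator, report robust fit indices, and replace the ordinary likelihood ratio test with the scaled chi-square difference test.
4. Keep the number of parameters below the number of families, for example by using subscale scores or parcels if item-level models are too large.
5. Apply the noninvariance rule only to these corrected tests.

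The cost is some SAP wording and a modest amount of model set-up, including separating the parent-only tests from the whole-model analysis. No new data are needed. Standard errors for parent-level paths become about 25-31% wider (√1.57 = 1.25; √1.71 = 1.31), which is their correct width under the assumptions above.

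### A scalar-only invariance failure would drop the between-arm mentalising-to-anger path comparison, which needs equal loadings only

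*SAP*

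**What the plan says.** The relevant text is in the SAP under Testing the theory of change mechanisms. The SEM is a multigroup model with MBT-PP and TAU as the groups. Three nested models are fitted: configural, metric and scalar. On the metric model the SAP says: "This is assessed by constraining the various factor loadings to be equivalent across the groups". On the scalar model: "This is assessed by specifying that item intercepts are equivalent across the groups". Likelihood ratio tests compare metric with configural and scalar with metric, and "If either of these two tests is significant then this suggests potential problems with measure noninvariance". No significance level is given for these two tests.

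The models are then to be explored for reasons for any noninvariance. The SAP adds: "In the case of noninvariance we might not be able to then compare the latent" means across the arms. It closes with the fallback: "In such a scenario we would test the models in each group separately and not directly compare any parameters across the two groups".

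The next paragraph sets the condition for going ahead: "If the assumption of measure invariance is upheld, we will look to compare latent means across group". Under that same condition comes the path comparison: "We would also compare the regression coefficients from the mentalising latent variables to the anger expression latent variable in a similar way". The procedure is reused for the well-being models, the separated-parent models and fathers' SDQ-TD.

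**The concern.** The two planned comparisons need different levels of invariance, but the plan gives them one gate. Equal intercepts are a requirement for comparing latent means, not for comparing regression coefficients. A scalar-only failure therefore removes a comparison whose validity it does not touch. The exploration step offers no way back, because no criterion is stated for continuing after it.

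Arm is the grouping variable, so MBT-PP versus TAU enters this SEM only through cross-arm comparisons. The mentalising-to-anger coefficient is the one path that the SAP names for such a comparison. If it is dropped, the report would show two arm-specific coefficients side by side with no test or interval for their difference.

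**Working it through.** The plan states no figure for this rule, so there is none to reproduce.

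**Step 1. What each comparison needs.** With items x = ν + Λη + ε, where κ is the latent mean vector and Φ the latent covariance matrix:

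- item means: E(x) = ν + Λκ
- item covariances: Cov(x) = ΛΦΛ′ + Θ

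Comparing κ between arms needs common ν and Λ. A path such as mentalising to anger is a function of Φ. It is identified from the covariances, which contain Λ but not ν. Equal loadings are enough.

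**Step 2. Numerical check of step 1.** A two-group maximum-likelihood SEM was fitted to population moments. It had 6 mentalising and 7 anger items, with assumed standardised loadings of 0.7 and a true path of −0.4 in both arms. Each invariance test has 13 − 2 = 11 df. Total N = 250, alpha 0.05.

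| Assumed truth in the MBT-PP arm | Metric test rejects | Scalar test rejects | Path dropped by the rule | Fitted paths, TAU / MBT-PP (metric model) | Path-difference test rejects |
|---|---|---|---|---|---|
| Full invariance | 5% | 5% | 9.8% | −0.400 / −0.400 | 5.0% |
| 2 intercepts +0.3 SD | 5% | 72.5% | 73.8% | −0.400 / −0.400 | 5.0% |
| 2 intercepts +0.5 SD | 5% | 99.8% | 99.8% | −0.400 / −0.400 | 5.0% |
| 2 loadings 0.7 to 0.4 | 67.0% | 5.5% | 68.8% | −0.378 / −0.433 | 6.7% |
| 3 loadings 0.7 to 0.35 | 89.5% | 6.1% | 90.2% | −0.366 / −0.481 | 11.6% |

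With equal loadings and shifted intercepts, the path is recovered exactly and its test keeps its 5% size. With unequal loadings the paths diverge falsely and the size rises. The metric test is therefore the right gate for paths.

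**Step 3. Cost under full invariance.** For two independent tests at 0.05, the path comparison is blocked with probability 1 − 0.95² = 0.0975. A metric-only gate blocks it with probability 0.05.

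**Step 4. Cost with intercept shifts on the PRFQ.**

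- From the Protocol (Secondary outcomes, f): 18 items, three subscales, alphas .69, .77 and .75.
- From SAP Table 2: 125 families per arm. With the 20% attrition case in the SAP's sample size section, 125 × 0.8 = 100.
- Assumed: 6 items per subscale, factor correlation 0.2, alpha 0.05, three items shifted in the same direction, loadings equal.

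The inter-item correlation is r = α/(6 − 5α) and the loading is √r:

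- .69/2.55 = 0.271, loading 0.52
- .77/2.15 = 0.358, loading 0.60
- .75/2.25 = 0.333, loading 0.58

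The noncentrality of the scalar test, with n per arm, Σ the item covariance matrix and δ the vector of shifts, is (n/2)·q, where q = δ′[Σ⁻¹ − Σ⁻¹Λ(Λ′Σ⁻¹Λ)⁻¹Λ′Σ⁻¹]δ.

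For 0.3 SD shifts, q = 0.332 with one shifted item in each subscale and 0.185 with all three in the first subscale. For 0.2 SD shifts both are multiplied by (0.2/0.3)² = 0.444, giving 0.148 and 0.082. A PRFQ-only test has 18 − 3 = 15 df. The SEM figures are not shown, so a wider test is illustrated with an assumed 76 items and 8 factors, 76 − 8 = 68 df.

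| n per arm | Shift | Noncentrality | Rejects, 15 df | Rejects, 68 df |
|---|---|---|---|---|
| 125 | 0.3 SD | 11.6 to 20.8 | 53% to 85% | 25% to 49% |
| 125 | 0.2 SD | 5.1 to 9.2 | 23% to 42% | 12% to 20% |
| 100 | 0.3 SD | 9.3 to 16.6 | 42% to 73% | 20% to 38% |

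The lower end of each range has all three items in one subscale; the upper end has one in each.

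**The case against.** The strongest reply is that little hangs on this. The Protocol calls the mediation models exploratory. The ITT analyses do not pass through this gate, and they already compare all three PRFQ subscales between arms for mothers and fathers. Arm-specific paths would still be estimated. The theory of change says that MBT-PP raises mentalising, which lowers anger; it does not require the slope to differ by arm. The comparison closest to that claim is of latent means, where a scalar gate is correct. All of this stands, and it limits the importance of the point. It does not make the gate right for the path.

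The wording is also softer than an automatic cancellation: a significant test signals potential problems, and an exploration comes before the fallback. That stands too, but without a criterion for continuing, a scalar-only failure still leads to no comparison.

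Four stronger readings are tempting and not supported:

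- **That the SAP predicts noninvariance in mentalising.** It says that, given random allocation, it would not expect the arms to interpret the constructs differently. The words "as the groups will have differing experiences during the intervention period, particularly in relation to aspects of mentalising" are its reason for checking.
- **That the loss is most likely where the therapy works.** This is an inference. If therapy changed loadings as well as intercepts, the metric test should tend to fail, and dropping the path comparison would be justified.
- **That a problem in one instrument cancels comparisons for all the others.** The SAP does not say whether testing is model-wide or by instrument.
- **That 175 per arm applies to the scalar test.** In the SAP, 175 is the number of children per arm; as a family count it is the superseded Protocol target. Parents complete the PRFQ, and the planned number is 125 families per arm.

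**Conclusion.** The point holds in a limited form. When the metric test passes and the scalar test fails, the SAP drops a path comparison that remains valid. When the metric test fails, the restriction is sound. That equal loadings suffice does not depend on any assumed value.

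How often the loss would occur does depend on assumptions: the 5% level, the number and size of intercept shifts, the factor structure and which items move. The excess is 4.75 percentage points (9.75% − 5%) under full invariance with independent tests. With the assumed shifts at 125 per arm, the scalar test rejects in anything from 12% (0.2 SD, 68 df, items in one subscale) to 85% (0.3 SD, 15 df, one item in each subscale). The documents do not say which case is likely.

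A reader might infer that every between-arm comparison in the trial is at risk. The documents do not support this: only direct comparisons of SEM parameters are affected. It is an inexpensive correction to an exploratory analysis.

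**What to change.** Replace the fallback sentence on noninvariance in the SAP with:

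> Regression coefficients will be compared across arms if metric invariance holds for the latent variables involved, whatever the scalar result. Latent means will be compared only if scalar invariance holds. If metric invariance fails for a latent variable, parameters involving it will be reported by arm and not compared directly.

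Amend the opening condition of the following paragraph to match, so that the mean comparison and the path comparison each carry their own requirement. State the significance level for both invariance tests. The same rule should apply wherever the procedure is reused.

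A partial-invariance analysis of latent means may be added as an optional step, labelled exploratory because it selects items from the data. It is not needed for this correction.

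The cost is SAP wording and at most a few extra lavaan fits, with no new data and no change to the primary analysis. The change should be made before SEM results by arm are seen, so that the choice of rule cannot look data-driven.
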